### 7.1 Study Timeline

This 12-month multicentre, prospective, observational study is to be conducted in 2 phases:

1. Patient recruitment, single-lead and 12-lead ECG recordings and data entry (9 months): Period recruitment will take place and ECG recording with wearable devices
2. Completion of data entry and analysis (3 months): to finalise the data entry, adjudicate all ECGs and perform the statistical analysis. A final wrap up meeting will be convened at the end of the study with all key investigative staff contributing to the final report and manuscript.

## 7.2 Study Risks

This study only involves performing a 12-lead ECG, which is standard of care, and two additional 30-second 1-lead ECG recordings with a SkyLabs CART-I ring and an Apple Watch.

There are no known contraindications for the SkyLabs CART-I ring or Apple Watch and potential adverse events only include skin reactions to the metal or silicone wrist band. The devices are only in place long enough to obtain two 30-second recordings, so this risk is negligible.

A 12-lead ECG is safe and painless. Removing the sensors from your skin may cause some slight discomfort and some people may develop a mild rash which usually resolves quickly.

To reduce the risk of infection, doctors and research nurses will wear appropriate personal protective equipment according to local infection control guidelines. Both wearable devices will be thoroughly cleaned with a Clinell® wipes before and after each use. A minimum of 10 minutes will elapse before the device is used in a different participant.

## 7.3 Study Benefits

The main benefit from this study will be for future patients. However, participants may get direct benefit from the study if the second (extra) 12-lead ECG records any heart rhythm abnormality that was not seen during the first 12-lead ECG. Both 12-lead ECGs (usual care and extra) will be added to the medical notes and available to the clinical team.

We anticipate that with widespread use of wearable devices with optical sensors and electrodes capable of recording and analysing PPG signals and 1-lead ECGs, will significantly increase the number of patients seeking expert medical opinion due to 'abnormal findings' by their device. It is therefore important to validate and understand the limitations of arrhythmia detection from commonly used wearable devices. Moreover, the new ESC guidelines on Management of Atrial Fibrillation recommended 1-lead ECG validation studies prior to widespread adoption.

## 8. PARTICIPANT IDENTIFICATION

### 8.1. Trial Participants

This trial is designed to include male and female adults attending cardiology outpatient clinics, outpatient investigations, catheterisation lab day unit or inpatients at a Heart Centre, having a routine 12-lead ECG.

## **8.2. Inclusion Criteria**

The participant must satisfy the following conditions:

- Participant is willing and able to give informed consent for participation in the trial.
- Male or female's aged 18 years or above.
- Indication for 12-lead ECG.

## **8.3. Exclusion Criteria**

The participant may not enter the study if ANY of the following apply:

- Unable to comply with instructions.
- Tattoos in the wrists or fingers where the device will be placed.
- Severe skin allergy to silicone (Apple Watch wrist band) or nickel allergies.

## **8.4. Recruitment**

The vast majority of patients attending the hospital for an outpatient cardiology clinic or procedure will have a routine 12-lead ECG performed as part of their standard care. Patients on the cardiology ward have routine daily 12-lead ECGs.

A participant information sheet will be given by the research team to patients attending a Heart Centre for outpatient appointments, investigation, catheterisation lab day unit, and to inpatient in a cardiology ward. Members to the research team are also members of the clinical care team. If the participants meet the inclusion criteria, they will be invited to participate in this study. An invitation letter may be sent in advance to patients attending the hospital for cardiac procedures.

## **8.5. Informed Consent**

The participant must personally sign and date the latest approved version of the Informed Consent form before any trial specific procedures are performed.

A written version of the Participant Information Sheet and Informed Consent form will be presented to the participants detailing no less than: the exact nature of the trial; what it will involve for the participant; the implications and constraints of the protocol; the known side effects and any risks involved in taking part. It will be clearly stated that the participant is free to withdraw from the trial at any time for any reason without prejudice to future care, without affecting their legal rights and with no obligation to give the reason for withdrawal.

Participants will be allowed until the end of their appointment and/or clinic to consider the information provided and the opportunity to question the investigator or other independent parties if they so wish. Patients admitted in the Cardiology/Cardiothoracic Wards will have until the end of their admission to decide if they want to participate. Written informed consent will then be obtained by means of participant dated signature and dated signature of the person who presented and obtained the Informed Consent. The person who obtained the consent must be suitably qualified and experienced and have been authorised to do so by the Chief/Principal Investigator. A copy of the signed Informed Consent will be given to the participant and a copy will be filed in the patients' medical note. The original signed form will be retained at the trial site. Screening, Eligibility and Baseline Assessment

After agreeing to participate and signing the consent form the baseline assessment will include demographics information and medical history.

## **8.6 Randomisation**

The order in which the wearable devices being investigated will be randomly assigned in a 1:1 fashion. There are two investigation arms:

- Group 1: SkyLabs CART-I ring and then Apple Watch
- Group 2: Apple Watch and then SkyLabs CART-I ring

A simple randomisation will be performed by using the Robust Randomisation app (RRapp, developed by Icahn School of Medicine Mount Sinai) which will assign each participant to either Group 1 or Group 2.

## **8.7 Blinding**

Investigators and subjects will not be blinded to investigation arms during data collection. At the end of the follow-up, all the anonymised ECGs (12-lead and 1-lead from wearables), from all sites, will be adjudicated by two cardiologists blinded to patients' data.

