## 7. STUDY DESIGN

This study is a prospective, multicentre, observational study comparing rhythm and heart rate detection of two novel wearable devices — the Skylab CART-I ring and Apple Watch Series 6 — to a 12-lead ECG (gold-standard) for different cardiac rhythm disorders. We will recruit 500 participants attending Cardiology outpatient appointments, procedures or investigations (including the catheterisation laboratory) and inpatients in the cardiology and cardiothoracic wards in three hospitals across the UK. All patients will be due a 12-lead ECG as part of their standard of care.

If participants agree to take part in this study, the research team will provide them with instructions and will demonstrate how to use the wearable devices. Participants will then be asked to perform a simultaneous 30-seconds 12-lead ECG and 1-lead ECG for each wearable device (Skylab CART-I ring or Apple Watch). The order of recordings will be randomly assigned. If the first recording is uninterpretable due to artefact, a second recording will be allowed.

[figure not shown]
The SkyLabs CART-I Ring generates a 30-second 1-lead ECG by placing the participants finger on the rings' metal casing. Similarly, the Apple Watch 1-lead ECG requires the participant to place his/her finger on the metal crown. The 1-lead ECGs will be displayed and saved in the CART-I ring app and Apple Health app of a research iPhone SE, respectively. The smartphone apps will not contain any identifiable data and participants will only be identified by the time stamp of their recordings. The clocks of the Apple Watch, SkyLabs CART-I ring and ECG machine will be synchronised. The 12-lead ECG will also contain a time stamp and the study ID number (site code and participant number), it will then be recorded by using the iPhone SE camera and exported in PDF format for subsequent analysis. The 12-lead ECGs time stamp will also be documented in the CRF. The 12-lead ECGs will be added to the participants medical notes and available to the clinical team. The 1-lead ECGs from the wearable devices will only be available to the research team.

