This study does not involve any follow-up visits. All the 1-lead ECGs stored in the CART-I Ring app and Apple Health app will be exported in PDF format. All ECGs (12-lead ECGs and 1-lead ECGs from the wearable devices) will be analysed by two Cardiologists (based at Oxford University Hospital NHS Foundation Trust/OUHFT) blinded to patient's data. Any disagreement will be resolved by a third Cardiologist (CI of the study).

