## **8.9. Wearable Devices**

The Apple Watch Series 6 will be worn snugly on the left or right wrist according to patient's preference. The participants will rest their arm comfortably on their lap. The investigator will open the ECG app on the Apple Watch. With the hand opposite to the watch the participant will be asked to hold their finger on the digital crown to generate a 30-second 1-lead ECG. During the same 30 seconds a simultaneous 12-lead ECG recording will be performed. The Apple Watch recording will be stored in the research iPhone SE Health app (with no identifiable data), uploaded to the iCloud and will be exported in PDF format for analysis.

The SkyLabs CART-I ring will be worn on the same hand as the Apple Watch, preferably in the ring finger. Similarly, a simultaneous 30-seconds recording with a 12-lead ECG will be performed with the participant resting his/her hand comfortably. A 30-second 1-lead ECG can be generated by placing a finger from the opposite hand on the metal casing and selecting the 'measure' tab in the CART-I ring app. The SkyLabs recording will be stored in the CART-I Ring app and uploaded to the SkyLabs CRM account (with no identifiable participant's data) and will be exported at a later date in PDF format for analysis.

If the first recording of any of the wearable devices has artefacts a second recording will be allowed, and the first recording discarded. The order of the devices will be randomly selected at the time of the baseline visit.

By enrolling in the study, participants will likely extend their hospital visit by 20-30 minutes to complete all study procedures. A minimum of 10 minutes will elapse before the device is used by a different participant.

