## 10 STATISTICS AND ANALYSIS

Descriptive statistics are reported as count and percentage for categorical variables and mean and standard deviation for continuous variables.

Adjudication of all anonymised ECGs (12-lead ECGs, 1-lead ECGs from Apple Watch and SkyLabs CART-I ring) will be performed by two Cardiologists blinded to participants' data. Any disagreements will be decided by a third Cardiologist (CI of the study). Following adjudication, the sensitivity, specificity, positive negative predictive values will be calculated for different cardiac rhythm disorders. The level agreement between adjudicators will be calculated using the Cohen's kappa.

ECG waveform analysis and intervals (PR, QRS, QT and RR) will be measured by using callipers to the nearest 0.25 mm. The first three consecutive waveforms will be analysed in each ECG and the intervals averaged. In the 12-lead ECG, it will be to the physician's discretion which lead is chosen to measure the

intervals. To investigate the level of agreement, correlation coefficient and Band-Altman plots will be generated.

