### **11.3 Data Recording and Record Keeping**

The participants will be identified by a unique study specific ID number (includes the site ID code and participant number) which will be assigned following consent. The study ID number (will be used in both hard-copies and electronic documents (PDF of 12-lead ECGs, excel spreadsheets for analysis and adjudication). The hard copies (CRF and consent forms) of data will be securely kept in the Research Fellows' Office at each site. The key to the study ID number for each site will be maintained on a single document will be kept in a separate folder in the PI's office.

The participants name and any other identifying detail will NOT be included in any trial data electronic file (PDF of 12-lead ECGs, 1-lead ECGs, excel spreadsheets for adjudication and analysis).

Each individual site will have an Apple Watch and SkyLabs CART-I rings (five different sizes) which will be paired with a research iPhone SE. No identifiable data will be recorded in the iPhone SE. Apple Watch 1-lead ECGs are transmitted to the research iPhone health app with no patient identifiable information. The time stamp on each ECG will be documented on the CRF and used to identify study participants. All the data pertaining to the Apple Watch will be stored in the research iPhone SE and uploaded to the iCloud so that it can be assessed remotely for adjudication. All 3 research iPhones (one per site) will be registered to a research account ([[contact]](mailto:[contact])) and thus all uploads to the iCloud can be accessed centrally by the investigators in OUHFT. Individual upload can be identified by the serial number for the CART-I rings and by the name of the Apple Watch (different for each site) and thus if there are two recordings with the same time stamp we can easily identify the site and match it to the matching 12-lead ECG.

The SkyLabs CART-I ring data is recorded to its app (CART-I smpl) in the iPhone SE and to a password protected Oxford CRM Skylab online account (<https://www.CART-Icardiotracker.com>; see Appendix C) created for the purpose of this study ([[contact]](mailto:[contact])). Only the investigators will have access to the

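### The plan does not keep the 1-lead reading independent of the paired 12-lead reading: the same two cardiologists read both, and neither masking of the pair nor a reading order is set

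*Combined protocol and SAP*

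**What the plan says.** Section 7 (Study Design) assigns index and reference to the same people: "All ECGs (12-lead ECGs and 1-lead ECGs from the wearable devices) will be analysed by two Cardiologists". The stated masking is to patient information only. Section 8.7 says that "all the anonymised ECGs (12-lead and 1-lead from wearables), from all sites, will be adjudicated by two cardiologists blinded to" patients' data, and Section 10 says adjudication "will be performed by two Cardiologists blinded to participants' data". For the tie-break, Section 10 adds: "Any disagreements will be decided by a third Cardiologist (CI of the study"). Neither Section 7 nor Section 10 states any blinding for that third reader.

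The two traces of a pair are closely tied. For the watch, Section 8.9 says: "During the same 30 seconds a simultaneous 12-lead ECG recording will be performed". It describes the same arrangement for the ring. Section 7 has the clocks of both wearables and the ECG machine synchronised. It also says: "The 12-lead ECG will also contain a time stamp and the study ID number (site code and participant number"). The wearable recordings carry only a time stamp as identifier. Section 11.3 makes that stamp the linking key: "The time stamp on each ECG will be documented on the CRF and used to identify study participants". The same section keeps the study ID on the 12-lead PDFs and in the spreadsheets used for adjudication.

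Section 8.7 places adjudication at the end, pooled over sites and on anonymised tracings. Section 7.1 allots three months to finishing data entry, adjudication and analysis.

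**The concern.** The index test here is a human judgement. The primary objective in Section 6 is the accuracy of physician interpretation of the 1-lead, so the estimate is valid only if that judgement is made without knowledge of the reference. Anonymising a tracing hides who the patient is. It does not hide the other tracing taken in the same 30 seconds, or the reading already given to it.

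A cardiologist who has seen the 12-lead, or can find it by its time stamp, may read an ambiguous strip in its light. That moves the 1-lead reading towards the reference and raises apparent sensitivity, specificity and predictive values. The secondary outcomes that rest on reader measurement or interpretation (intervals, and the ring's 1-lead with the PPG signal added) are exposed in the same way. Influence in the other direction, from strip to 12-lead, would also touch the reference used for automatic AF detection.

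No later analysis can repair this, because once a strip has been read with knowledge of its 12-lead, the unaided reading is lost. The planned Cohen's kappa between adjudicators would not reveal it, since the same 12-lead can sway both readers.

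**Working it through.** The plan gives no figure to reproduce: the 500 participants come without an expected accuracy, prevalence or precision target. The check has two parts.

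**1. What the plan masks**

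| Safeguard | Stated in the plan? |
|---|---|
| Patient identity and data hidden from the two readers | Yes (Sections 7, 8.7, 10) |
| Adjudication pooled over sites at the end | Yes (Section 8.7) |
| 1-lead readers masked to the paired 12-lead and its reading, or the reverse | No |
| Time stamps and study IDs removed or recoded before reading | No; Section 11.3 keeps the study ID on the 12-lead PDFs |
| Reading order, separate sessions, locking of 1-lead reads | No |
| Different readers for index and reference | No; the same two |
| Any masking of the third cardiologist | No |

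Workload: 500 participants × (two 12-leads + two 1-leads) = 2,000 tracings. With two readers, that is 2,000 × 2 = 4,000 readings.

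**2. How large the effect could be (illustration only)**

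Let p be the accuracy of unaided reading, and s the share of would-be errors that are corrected because the reader recognises the pair. Then

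observed accuracy = p + s(1 − p).

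The documents give no value for s. For p, the one relevant figure is in Section 5: 96% sensitivity and 100% specificity for AF from interpretation of the Apple Watch 1-lead PDF, in a study of 50 patients after cardiac surgery. The other values of p below are assumptions.

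| p | s = 25% | s = 50% | Gain in points |
|---|---|---|---|
| 70% (assumed) | 77.5% | 85.0% | 7.5 to 15 |
| 85% (assumed) | 88.75% | 92.5% | 3.75 to 7.5 |
| 96% (Section 5) | 97.0% | 98.0% | 1 to 2 |
| 100% (Section 5, specificity) | 100% | 100% | 0 |

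For example, 0.85 + 0.25 × 0.15 = 0.8875, and 0.96 + 0.50 × 0.04 = 0.98.

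The same formula applies to specificity with its own p, and the predictive values follow. With assumed sensitivity 80%, specificity 90% and prevalence 20%, PPV is 0.16/(0.16 + 0.08) = 0.667. At s = 25%, sensitivity is 85% and specificity 92.5%, so PPV = 0.17/(0.17 + 0.06) = 0.739. At s = 50% they are 90% and 95%, so PPV = 0.18/(0.18 + 0.04) = 0.818.

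The formula can only move accuracy upward, by construction. It shows scale and is not evidence that the bias will occur.

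**The case against.** The strongest reply is that the plan is silent, not wrong. It does not say that readers will see pairs together, or that time stamps stay visible on the files they read. Pooled, delayed reading of some 2,000 anonymised tracings makes recall of a particular pair less likely than bedside reading would. Since the time stamp identifies the participant, blinding to patients' data might be meant to cover it. Using the same readers for both traces is also defensible, because it separates the effect of the lead set from differences between readers.

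Much of this stands. A reader might infer that the 1-lead reading is in fact contaminated; the documents do not show that. What they show is that nothing prevents it. Delay weakens recall but does not stop matching by time stamp. The generous reading of the blinding statement sits badly with Section 11.3, which retains the study ID on the 12-lead PDFs and in the adjudication spreadsheets.

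A reader might also infer from Section 8.7 that the chief investigator, as tie-breaker, is unblinded to the rhythm. The text does not support this. What investigators are not blinded to is the investigation arm, and Section 8.6 defines the arms as device order. Knowing the order does not reveal the 12-lead rhythm. The supportable point is narrower: no masking is stated for the third reader.

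Finally, the size may be small. At the AF accuracy quoted in Section 5 there is little or no room for inflation. The documents give no accuracy figure for physician reading of other arrhythmias, so the same cannot be assumed for them.

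**Conclusion.** The concern holds as a missing safeguard on the primary outcome. Followed as written, the plan leaves the index reading open to influence from its own reference, through shared readers, linkable pairs and no set order. Confidence is high in the omission and low in the size of any bias. The gain in sensitivity at s between 25% and 50% runs from 1 to 2 points at p = 96% to about 4 to 7.5 points at p = 85%. It is zero where unaided accuracy is 100%. Every value of s, and every p except the two from Section 5, is an assumption.

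The point deserves action before adjudication because the harm would be irreversible and prevention is cheap. It does not affect the sample size.

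**What to change.** Add an adjudication procedure to Sections 8.7 and 10, in force before the first tracing is read:

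- Staff who do not read ECGs replace time stamps and study IDs on every tracing with random codes. They hold the linkage list, so that previously unknown abnormal rhythms can still be reported as Section 8.8 requires.
- Any automatic rhythm classification is masked if it is printed on the export. The example exports are not visible in the text reviewed, so this needs checking.
- The 1-lead strips are presented in random order. Those reads, including tie-breaks, are locked before any 12-lead is opened.
- The 12-leads are read in a separate, later session in a different order. The sponsor should state the interval.
- The third cardiologist works under the same masking.

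The cost is staff time to recode about 2,000 tracings and to fit two reading sessions into the three-month phase of Section 7.1. No extra reader or participant is needed.

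The limit should be stated in the report: this removes bias from recognising a pair. It does not remove a reader's systematic misclassification that appears on both traces, which would still count as agreement.

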## **15.8 Funding**

This trial will be partially supported by the Cardiac Rhythm Management Research Hub and SkyLabs grant for consumables and an Abbott Educational Grant.

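### No masking of the ECG readers to device is specified, so knowing whose device made a strip could colour the rhythm readings behind the primary accuracy estimates

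*Combined protocol and SAP*

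**What the plan says.** Adjudication is described in three places, and each limits the blinding to information about the patient.

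- Section 8.7: the anonymised ECGs "will be adjudicated by two cardiologists blinded to patients' data". The same section says "Investigators and subjects will not be blinded to investigation arms during data collection"; the arms are the two orders in which the devices are used.
- Section 10: adjudication "will be performed by two Cardiologists blinded to participants' data".
- Section 7: both cardiologists are blinded to the patient's data, in similar words.

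The deciding reader is the chief investigator. Section 7 says "Any disagreement will be resolved by a third Cardiologist (CI of the study" and Section 10 says "Any disagreements will be decided by a third Cardiologist (CI of the study" (closing bracket omitted in both quotes). Neither sentence states any masking for that reader.

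On the material to be read, Section 7 says "All the 1-lead ECGs stored in the CART-I Ring app and Apple Health app will be exported in PDF format". Section 8.9 repeats this for each device. Section 11.3 adds that the ring's PPG recordings are exported along with its ECGs. No section describes cropping, reformatting, recoding or shuffling the exports before they are read.

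On funding, the Synopsis lists the ring's maker among three funders. Section 15.8 says the study is "partially supported by the Cardiac Rhythm Management Research Hub and SkyLabs grant for consumables and an Abbott Educational Grant". The Watch's maker is not listed.

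**The concern.** The primary outcome in Section 6 is the sensitivity, specificity and predictive values of a physician's reading of each device's strips. That reading is a judgement. The plan expects disagreement, since it measures kappa and names a tie-breaker, and it gives no written criteria for the rhythm categories or for calling a strip uninterpretable.

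A reader who knows which device made a strip may give a doubtful trace a more generous call, or set it aside as uninterpretable more readily, for one device than for the other. This does not require bad faith. A larger sample would not remove such a bias, and it could not be corrected afterwards without reading the strips again. Because one maker contributes funds and the other does not, even an unbiased result would be easier to challenge.

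The protections already in the plan do not cover this. Blinding to patient data leaves the device visible. Randomising the order of the devices (Section 8.6) treats them evenly when recordings are made, but not when they are read.

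**Working it through.** **Step 1: what is masked, and for whom.**

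| Reader | Masked to patient data | Masked to device |
|---|---|---|
| Two cardiologists (Sections 7, 8.7, 10) | Yes | Not stated |
| Chief investigator as third reader (Sections 7, 10) | Not stated | Not stated |

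The word anonymised does not fill the gap. Where the plan explains it (Sections 7 and 11.3), it concerns the participant's identity.

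**Step 2: could a reader recognise the device?** The caption in the ring appendix describes an example with a PPG signal as well as the ECG. The caption in Appendix D describes a Watch export that carries a date of birth from the profile. If the exports reach the readers unaltered, either feature would identify the device without a logo. The pages themselves are not shown, so recognition is likely but not established.

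**Step 3: size.** The plan gives no figure to reproduce. It states 500 participants with no expected prevalence, sensitivity, precision target or margin. What follows is for scale only, and every input except the 500 is an assumption.

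Spurious gap between the devices = (share of strips that are borderline) × (difference between devices in how often borderline strips are called correctly).

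- Low end: 5% borderline, 10-point difference: 0.05 × 0.10 = 0.005, or 0.5 points.
- Middle: 10% and 20 points: 0.10 × 0.20 = 0.02, or 2 points.
- High end: 20% and 30 points: 0.20 × 0.30 = 0.06, or 6 points.

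For comparison, the sampling error of one device's sensitivity (Se) with D affected participants has 95% half-width 1.96 × √(Se(1 − Se)/D). With an assumed prevalence of 10% to 40%, D = 500 × 0.10 = 50 up to 500 × 0.40 = 200.

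- D = 50, Se = 0.90: 1.96 × √(0.09/50) = 0.083, or 8.3 points.
- D = 200, Se = 0.95: 1.96 × √(0.0475/200) = 0.030, or 3.0 points.

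The low end of the bias is small beside the sampling error (0.5 against 3.0 to 8.3 points). The high end is comparable with it (6 points).

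**Step 4: the work involved.** 500 participants × 2 devices = about 1,000 strips.

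**The case against.** Four points can fairly be made against this.

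1. The plan is silent; it does not say that the readers will know the device. A reader might infer that the device is visible on every strip. The documents do not support that: they describe how files are exported, not what is put before the reader, and the example pages cannot be seen. This stands, and the point is worded accordingly.
2. The plan sets each device against the 12-lead ECG. It has no ring-versus-Watch test, ranking or margin. A reader might infer that a few doubtful strips could reverse the order of the two devices. With 50 affected participants, five strips all resolved one way would move sensitivity by 5/50 = 10 points. But that takes a low case count, several borderline strips and every one falling the same way, all of it assumed, and it harms a comparison that the plan does not make. This stands too. What is left is possible bias in each device's own estimate and in any informal comparison.
3. The funding link is modest. The maker's part is a "SkyLabs grant for consumables", one of three sources, and the documents state no personal interest for any reader. Two readers would have to lean the same way to produce a biased agreed reading, and the chief investigator rules only where they differ. This lowers the likelihood but does not remove the gap: readers who share an expectation can agree with each other, and kappa does not detect a shared lean.
4. Removing the PPG from every strip would conflict with secondary objective 4, which compares the ring's ECG alone with the ECG and PPG combined. This is right, and the fix must provide for it.

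**Conclusion.** The concern holds as an omission: the plan specifies no masking to device for either reader or for the chief investigator, and the primary outcome rests on their judgement. The likely harm is bias in each device's accuracy against the 12-lead ECG, and in any side-by-side reading of the two.

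The size cannot be estimated from the documents. The range of 0.5 to 6 points depends wholly on the assumed share of borderline strips (5% to 20%) and the assumed difference in how they are called (10 to 30 points). Nothing in the documents shows that bias will occur, or that the funding would cause it. The change is still worth making, because it is cheap, needs no extra reader and is best made before adjudication begins.

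**What to change.** Amend Sections 7, 8.7 and 10 before any strip is read.

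- For the primary ECG-only reading, crop each exported 1-lead strip to the waveform, scale and calibration in one common layout, with no logo, product name, profile text or PPG channel.
- Give each strip a code and read ring and Watch strips in one mixed random order.
- State that the two cardiologists and the chief investigator, when deciding disagreements, are masked to device as well as to patient data.
- Have a team member who does not read hold the key. Section 11.3 matches recordings to participants by time stamp, which cropping would remove, so the key must link each code to device, time stamp and study ID.
- Do the ring ECG-plus-PPG reading for secondary objective 4 separately, after the primary reading is locked, and report it as not masked to device.

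The cost is file preparation for about 1,000 strips and a short addition to each of the three sections. Masking may be incomplete, because the style of the trace may still reveal the device; the report should state this as a limitation.
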